### **AEs considered “Always Serious”**

Cancers of new histology and exacerbations of existing cancer must be reported as a serious event regardless of the duration between discontinuation of the drug and the occurrence of the cancer.

In accordance with the European Medicines Agency initiative on Important Medical Events, Boehringer Ingelheim has set up a list of further AEs, which by their nature, can always be considered to be “serious” even though they may not have met the criteria of an SAE as given above.

The latest list of “Always Serious AEs” can be found in the RDC system. These events should always be reported as SAEs as described in [Section 5.3.7](#).

### **Adverse events of special interest (AESIs)**

The term AESI relates to any specific AE that has been identified at the project level as being of particular concern for prospective safety monitoring and safety assessment within this trial, e.g. the potential for AEs based on knowledge from other compounds in the same class. AESI need to be reported to the Sponsor’s Pharmacovigilance Department within the same timeframe that applies to SAE, see [Section 5.3.7](#).

The following are considered as AESIs: adverse events relating to gastrointestinal perforation and hepatic injury.

#### Hepatic Injury

In this study protocol, hepatic injury is defined as follows:

- ALT and/or AST  $\geq$  8 fold ULN
- ALT and /or AST  $\geq$  3 fold ULN and total bilirubin  $\geq$  2 fold ULN\*
- ALT and /or AST  $\geq$  3 fold ULN and unexplained INR  $>$  1,5\*
- ALT and /or AST  $\geq$  3 fold ULN and unexplained eosinophilia ( $>$ 5%)\*
- ALT and /or AST  $\geq$  3 fold ULN and appearance of fatigue, nausea, vomiting, right upper abdominal quadrant pain or tenderness, fever and/or rash

\* in the same blood draw sample.

These lab findings constitute a hepatic injury alert and the patients showing these lab abnormalities need to be followed up according to the “DILI checklist” provided in the ISF.

In case of clinical symptoms of hepatic injury (icterus, unexplained encephalopathy, unexplained coagulopathy, right upper quadrant abdominal pain, etc.) without lab results (ALT, AST, total bilirubin) available, the investigator should make sure these parameters are analysed, if necessary in an unscheduled blood test. Should the results meet the criteria of hepatic injury alert, the procedures described in the DILI checklist should be followed.

### **Intensity of AEs**

The intensity of the AE should be judged based on the following:

- Mild: Awareness of sign(s) or symptom(s) that is/are easily tolerated  
Moderate: Enough discomfort to cause interference with usual activity  
Severe: Incapacitating or causing inability to work or to perform usual activities

The intensity of **diarrhea adverse events** should in addition be classified and recorded in the (e)CRF according to the Common Terminology Criteria for Adverse Events (CTCAE) version 4 [[R10-4848](#)].

Table 5.3.6.1:1 CTCAE Categorization for diarrhea

CTCAE Grade	
1	Increase of <4 stools per day over baseline
2	Increase of 4 to 6 stools per day over baseline
3	Increase of $\geq 7$ stools per day over baseline; incontinence
4	Life threatening consequences
5	Death

### **Causal relationship of AEs**

The definition of an adverse reaction implies at least a reasonable possibility of a causal relationship between a suspected medicinal product and an adverse event. An adverse reaction, in contrast to an adverse event, is characterised by the fact that a causal relationship between a medicinal product and an occurrence is suspected.

Medical judgment should be used to determine the relationship, considering all relevant factors, including pattern of reaction, temporal relationship, de-challenge or re-challenge, confounding factors such as concomitant medication, concomitant diseases and relevant history.

Arguments that may suggest that there is a reasonable possibility of a causal relationship

could be:

- The event is consistent with the known pharmacology of the drug
- The event is known to be caused by or attributed to the drug class.
- A plausible time to onset of the event relative to the time of drug exposure.
- Evidence that the event is reproducible when the drug is re-introduced
- No medically sound alternative aetiologies that could explain the event (e.g. preexisting or concomitant diseases, or co-medications).
- The event is typically drug-related and infrequent in the general population not exposed to drugs (e.g. Stevens-Johnson syndrome).
- An indication of dose-response (i.e. greater effect size if the dose is increased, smaller effect size if dose is diminished).

Arguments that may suggest that there is no reasonable possibility of a causal relationship could be:

- No plausible time to onset of the event relative to the time of drug exposure is evident (e.g. pre-treatment cases, diagnosis of cancer or chronic disease within days / weeks of drug administration; allergic reaction weeks after discontinuation of the drug concerned)
- Continuation of the event despite the withdrawal of the medication, taking into account the pharmacological properties of the compound (e.g. after 5 half-lives). Of note, this criterion may not be applicable to events whose time course is prolonged despite removing the original trigger.
  - Additional arguments amongst those stated before, like alternative explanation (e.g. situations where other drugs or underlying diseases appear to provide a more likely explanation for the observed event than the drug concerned).
  - Disappearance of the event even though the study drug treatment continues or remains unchanged.

For Japan only: The reason for the decision on causal relationship for unlisted AEs needs to be provided in the eCRF.

### 5.3.7 Adverse event collection and reporting

[figure not shown]
#### AE Collection

The Investigator shall maintain and keep detailed records of all AEs in their patient files. The following must be collected and documented on the appropriate CRF(s) / eCRF by the Investigator:

- From signing the informed consent onwards through the Residual Effect Period (REP), until individual patient's end of trial:
  - all AEs (serious and non-serious) and all AESIs.

However, if an individual patient discontinues trial medication prematurely but stays in the trial (i.e. if further visits incl. telephone visits, or vital status assessments are planned) from then on and until the individual patient's end of the trial the Investigator must report related SAEs and related AESIs.

- After the individual patient's end of trial: the investigator does not need to actively monitor the patient for AEs but should only report relevant SAEs and relevant AESIs of which the investigator may become aware of.

The Residual Effect Period (REP) is defined as 28 days after the last trial medication application. All AEs which occurred through the treatment phase and throughout the REP will be considered as on treatment please see [Section 7.3.4](#). Events which occurred after the REP will be considered as post treatment events.

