Adverse events will be collected, documented and reported from the time the patient signs an Informed Consent up until 28 days after the last dose of study medication.

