#### **7.3.4 Safety analyses**

Adverse events will be coded using the Medical Dictionary for Regulatory Activities (MedDRA) coding dictionary. Standard BI summary tables and listings will be produced. All adverse events with an onset between start of treatment and end of the residual effect period (REP), a period of 28 days after the last dose of trial medication, will be assigned to the treatment period for evaluation. All treated patients will be included in the safety analysis. In general, safety analyses will be descriptive in nature and will be based on BI standards. No hypothesis testing is planned.

Statistical analysis and reporting of adverse events will concentrate on treatment-emergent adverse events. To this end, all adverse events occurring between start of treatment and end of the residual effect period will be considered 'treatment-emergent'. The residual effect period is defined as 28 days. Adverse events that start before first drug intake and deteriorate under treatment will also be considered as 'treatment-emergent'.

Frequency, severity, and causal relationship of adverse events will be tabulated by system organ class and preferred term after coding according to the current version of the Medical Dictionary for Drug Regulatory Activities (MedDRA).

Laboratory data will be analysed both quantitatively as well as qualitatively. The latter will be done via comparison of laboratory data to their reference ranges. Values outside the reference range as well as values defined as clinically relevant will be highlighted in the listings. Treatment groups will be compared descriptively with regard to distribution parameters as well as with regard to frequency and percentage of patients with abnormal values or clinically relevant abnormal values.

Vital signs, physical examinations, or other safety-relevant data observed at screening, baseline, during the course of the trial and at the end-of-trial evaluation will be assessed with regard to possible changes compared to findings before start of treatment.

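### Protocol Section 5.3.7 reduces AE reporting from the moment of early discontinuation, with no exemption for the 28-day residual effect period that other sections collect and analyse in full

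*Protocol*

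**What the plan says.** Under AE Collection, Protocol Section 5.3.7 gives a general rule and then an exception.

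- **General rule.** The period is "From signing the informed consent onwards through the Residual Effect Period (REP), until individual patient's end of trial", and the scope is "all AEs (serious and non-serious) and all AESIs".
- **Exception.** It opens with *However* and applies "if an individual patient discontinues trial medication prematurely but stays in the trial". Staying in the trial includes having only telephone contacts or vital status checks still planned. For these patients, "from then on and until the individual patient's end of the trial the Investigator must report related SAEs and related AESIs".
- **REP.** "The Residual Effect Period (REP) is defined as 28 days after the last trial medication application". The section adds: "All AEs which occurred through the treatment phase and throughout the REP will be considered as on treatment".

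Other places bear on the same days:

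- Protocol Section 3.1 has AEs collected from consent "up until 28 days after the last dose of study medication", with no separate rule for early discontinuers.
- Protocol Section 6.2.3 (Premature withdrawal) asks for an early end-of-treatment visit and then invites the patient to every remaining visit with all procedures. The visit lists in Section 6.2.2 have staff go through and document every AE.
- Protocol Section 7.3.4 states that "all adverse events occurring between start of treatment and end of the residual effect period will be considered 'treatment-emergent", with the residual effect period set at 28 days.
- SAP Section 7.8.1 uses the same 28 days after last intake and repeats the AE analysis with a 7-day limit.

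**The concern.** The exception ties reduced reporting to the discontinuation and not to the end of the REP. The days straight after an early stop then fall under two incompatible rules: collect all AEs, or report only related SAEs and related AESIs. The analysis assumes the first rule.

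If a site applies the second, the AE tables count a period in which part of the events was never requested. Several SAP safety groupings, such as MACE and bleeding in Table 7.8.1: 1, are defined by event terms and not by relatedness. A filter on relatedness at collection would therefore remove events those tables are meant to show.

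The exception reaches most early discontinuers. Vital status follow-up alone is enough to bring a patient under it, and Section 6.2.3 seeks week 52 vital status from those who decline further visits.

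**Working it through.** The plan gives no figure to reproduce, so the check is a comparison of texts.

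**Step 1: when does the exception start?** The sentence names one event before its time reference, the premature discontinuation of trial medication. It does not mention the REP. As written, reduced reporting starts at discontinuation.

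**Step 2: does the exception restrict?** The general rule already requires all AEs and all AESIs. A sentence opening with *However* that only added related SAEs and related AESIs would change nothing. It has effect only as a restriction.

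**Step 3: what applies on days 1 to 28 after an early stop?**

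| Place | Rule for those days |
|---|---|
| Protocol 5.3.7, general rule | all AEs, all AESIs |
| Protocol 5.3.7, exception | related SAEs, related AESIs |
| Protocol 5.3.7, REP definition | all AEs count as on treatment |
| Protocol 3.1 | AEs collected |
| Protocol 6.2.2 and 6.2.3 | all AEs documented at visits attended |
| Protocol 7.3.4 and SAP 7.8.1 | all AEs analysed as treatment-emergent |

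The exception is the only entry that departs from full collection.

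**Step 4: what could be omitted?** Full scope minus exception scope leaves non-serious AEs other than related AESIs, and SAEs judged unrelated.

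**Step 5: how much of the analysis window is exposed?** For a patient with t days on drug and w days counted after the last dose, the share of the treatment-emergent window governed by the exception is w / (t + w). The stopping times below are assumptions chosen to show a range.

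| Stop at | w = 28 | w = 7 |
|---|---|---|
| day 28 (week 4) | 28/56 = 50% | 7/35 = 20% |
| day 84 (week 12) | 28/112 = 25% | 7/91 = 8% |
| day 182 (week 26) | 28/210 = 13% | 7/189 = 4% |

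These are shares of days for one patient. They are not shares of AEs, and they say nothing about how many patients stop early. The 7-day repeat reduces the exposed share but does not remove it, because its extra days also follow the last dose.

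**The case against.** The best defence is that reduced reporting was meant to begin after the REP. That reading reconciles every passage, and the sentence does not contain the word *only*, whereas the next bullet, on the time after the patient's end of trial, does. The intention is plausible. The text does not state it, and Step 2 shows that the sentence does nothing unless it restricts.

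Two sources that might settle the timing cannot be consulted: the figure that opens Section 5.3.7 is not shown, and the flow chart is only partly available. A clear figure would help sites, but the sentence would still have to agree with it.

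Sections 3.1, 6.2.2 and 6.2.3 point sites towards full recording, and Section 5.3.7 itself asks for detailed records of all AEs in the patient files. This stands. Many sites may record everything, so one cannot say that data will be lost, only that the exception permits it.

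A reader might also infer more than the documents support:

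- *That AEs causing discontinuation are missed.* They begin before the last dose, so the full rule covers them on any reading.
- *That nintedanib events are under-counted relative to placebo.* This would need different stopping rates by arm, and none are given.
- *That relatedness judgements bias the open-label phase.* That phase has a single active arm, and sites stay blinded to the earlier allocation. The documents give no basis for a direction of bias.

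Finally, SAP Table 6.1: 1 ends the on-treatment safety period at 28 days after last intake or at end of treatment, whichever is first, which could be read as a shorter window. The text of SAP Sections 6.1 and 7.8.1 nevertheless counts safety data through the 28-day post-treatment period, as does Protocol 7.3.4. Safety analyses are descriptive, so no hypothesis test is affected.

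**Conclusion.** The point holds as an internal contradiction. The exception in Protocol Section 5.3.7, as written, starts at discontinuation and conflicts with the general rule and REP definition beside it, with Sections 3.1, 6.2.2, 6.2.3 and 7.3.4, and with SAP Section 7.8.1. If followed literally, it could leave treatment-emergent AE counts incomplete for early discontinuers in both the 28-day and the 7-day analyses.

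The size cannot be determined. It depends on how many patients stop early, when they stop, and which rule each site applies, and the documents give none of these. The 50% for a week 4 stop is one illustrative share of days and should not be read as an expected loss of events. Whether the arms would be affected differently is also unknown. The conclusion assumes that the figure in Section 5.3.7 does not already limit the exception to the time after the REP. If it does, figure and sentence still need to be aligned.

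**What to change.** Amend Protocol Section 5.3.7 along these lines: for every patient, including after premature discontinuation, all AEs, SAEs and AESIs are collected through 28 days after last intake; only from then until the patient's end of trial is reporting limited to related SAEs and related AESIs. Check that the figure in Section 5.3.7 and the flow chart show the same timing.

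The cost is one sentence and a clarification to sites. Discontinuers already have an early end-of-treatment visit and are invited to the scheduled visits. For those who decline further visits, the text describes only the week 52 vital status contact, so unless the flow chart already provides one, a contact about 28 days after last intake would be needed to complete the collection. The treatment-emergent definitions in Protocol 7.3.4 and SAP 7.8.1 need no change.

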### AE reporting to sponsor and timelines

The Investigator must report SAEs, AESIs, and non-serious AEs which are relevant for the reported SAE or AESI, on the BI SAE form via fax immediately (within 24 hours ) to the Sponsor's unique entry point (country specific contact details will be provided in the ISF).

The same timeline applies if follow-up information becomes available. In specific occasions the Investigator could inform the Sponsor upfront via telephone. This does not replace the requirement to complete and fax the BI SAE form.

For Japan only: All SAEs must be reported immediately to the head of the trial site.

With receipt of any further information to these events, a follow-up SAE form has to be provided. For follow-up information the same rules and timeline apply as for initial information.

### Information required

For each AE, the Investigator should provide the information requested on the appropriate (e)CRF pages and the BI SAE form. The Investigator should determine the causal relationship to the trial medication.

The following should also be recorded as an (S)AE in the (e)CRF and SAE form (if applicable):

- Worsening of the underlying disease or of other pre-existing conditions

- Changes in vital signs, ECG, physical examination and laboratory test results, if they are judged clinically relevant by the Investigator.

If such abnormalities already pre-exist prior trial inclusion they will be considered as baseline conditions.

All (S)AEs, including those persisting after individual patient's end of trial must be followed up until they have resolved, have been sufficiently characterized, or no further information can be obtained.

### **Pregnancy**

In rare cases pregnancy may occur in a clinical trial. Once a patient has been enrolled into this clinical trial and has taken trial medication, the Investigator must report immediately (within 24 hours) a potential drug exposure during pregnancy (DEDP) to the sponsor's unique entry point (country-specific contact details will be provided in the ISF). The Pregnancy Monitoring Form for Clinical Trials (Part A) should be used.

The outcome of the pregnancy associated with the drug exposure during pregnancy must be followed up and reported to the Sponsor's unique entry point on the Pregnancy Monitoring Form for Clinical Trials (Part B).

The ISF will contain the Pregnancy Monitoring Form for Clinical Trials (Part A and B).

As pregnancy itself is not to be reported as an AE, in the absence of an accompanying SAE and/or AESI, only the Pregnancy Monitoring Form for Clinical Trials and not the SAE form is to be completed. If there is an SAE and/or AESI associated with the pregnancy an SAE form must be completed in addition.

## **5.5 ASSESSMENT OF EXPLORATORY BIOMARKER(S)**

Blood samples will be taken according to the [Flow Chart](#) for the analysis of exploratory biomarkers.

These samples will be stored for up to 3 years after the end of the clinical trial.

Samples will be shipped from the sites to a central laboratory for short-term storage. These samples will be shipped in batches from the central laboratory to Boehringer Ingelheim or to another location for biomarker analyses or long-term storage.

In order to better understand the effects of nintedanib on the disease, mechanistic and disease related biomarkers will be assessed in peripheral blood of randomised patients.

The assessment of exploratory biomarkers is a key feature of this clinical trial with the aim to better characterise and understand the disease, as well as their potential predictive value for treatment response. All biomarkers related to IPF pathology will be explored pre during and post treatment with nintedanib or placebo in serum and plasma and will be correlated with the clinical endpoints.

## **Methods and timing of sample collection**

Whole blood will be collected for the preparation of serum, plasma and Collection time points are outlined in the Flowchart and respective footnotes. Correct, complete and legible documentation of drug administration and blood sampling times is mandatory to obtain data of adequate quality for biomarker analysis. A detailed description of biomarker sample collection and sample handling is provided in the ISF.

The samples will be shipped to the central laboratory and later analysed at the sponsor or a contractor of the sponsor.

### **5.5.1 Analytical determinations**

The analytical methods for the analysis of biomarkers from blood will be given in detail in a analytical biomarker report.

### **5.5.2 Biobanking**

To allow for future scientific analyses, all patients will be asked for additional samples. Only if a separate specific informed consent is given in accordance with local ethical and regulatory requirements, DNA and/or serum banking samples will be taken, processed and stored. Participation in the DNA and/or serum banking part is voluntary and not a prerequisite for participation in the study.

### **Serum banking**

To enable future not yet specified biomarker analyses additional blood will be collected into serum collection tubes. This sample will be collected according to the [Flow Chart](#). Details on sample collection and processing will be given in the ISF. This sample will be stored up to 15 years after the end of the trial and may be used for further characterization of IPF patients. Approximately 100 mL of blood will be collected for serum banking. Detailed instructions for serum banking sampling, handling and shipment of samples are provided in the ISF.

### **DNA banking**

The DNA sample derived from the original blood sample will be stored by Boehringer Ingelheim for up to 15 years after the end of the clinical trial or until there is no more material available for tests. The stored DNA may be used at a later time for pharmacogenomic analyses.

### **Methods and timing of DNA banking sample collection**

An amount of approximately 8.5 mL blood will be collected per PaxGene DNA blood sampling tube for those patients who signed a separate informed consent concerning the Sample DNA banking part with any other blood sampling after randomisation. The Paxgene Blood DNA tubes can be stored and shipped at room temperature within 14 days. If a longer storage and shipment period for Paxgene Blood DNA tubes is necessary, the blood samples have to be stored at a temperature of approximately -20°C or below. Once frozen, thawing of the samples should be avoided except for analysis. Detailed instructions for pharmacogenomics sampling, handling and shipment of samples are provided in the ISF.

